Once potential subjects have had time to review the consent document, they will meet with a study provider (MD or NP) that will explain the study, answer any questions, and administer informed consent. In the event that a volunteer is a patient of one of the study MDs or NPs, another staff MD or NP will answer questions and administer consent. Their designated contact will also have to meet with a study provider to hear what will be required of them if the subject participates in the study. Designated contact consent will be obtained in person or over the phone. Designated contact participants must have their own telephone in order to participate, either a personal cell phone or a household phone. If the designated contact's consent is obtained over the phone, two copies of the consent form will either be mailed or sent electronically to the designated contact (one to keep and one to return) and he/she will have the form in front of him/her during the phone consent process. The designated contact will return the signed consent form to the study staff either by mail or electronically, and the person obtaining informed consent will sign the document upon receiving it. All designated contacts will be trained in the symptoms of hypoglycemia and response to severe hypoglycemia, including the administration of glucagon. They will also be trained to recognize the symptoms of hyperglycemia, and when to contact study staff and local EMS. There will be separate consent documents for the subject and the designated contact. A licensed physician investigator will be available to speak with the subjects during the consent process in the event of an NP administering consent.

Study staff will answer any questions that the subjects and designated contacts may have during their participation. They will share any new information in a timely manner that may be relevant to the subject's willingness to continue participating in the trial. The subjects or designated contacts may choose to discontinue their participation at any time. If the designated contact chooses to discontinue their participation, another contact must be available, or study staff will make alternative arrangements to allow the subject to continue their participation in the study.

All enrollment and screening procedures and inclusion and exclusion criteria are the same for the Test Run and the RCT portion of the study.

V. Study Procedures

V. a. Screening Data

- Age
- Sex
- Race and ethnicity

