- There are no restrictions of any kind on diet or exercise in all three arms in the RCT portion of the study and the Test Run period, although subjects should attempt to maintain similar dietary habits and exercise habits during each arm of the study. The bionic pancreas must be kept dry during exercise.
- Subjects may choose to withdraw from the study at any time. If they withdraw from the study, they should contact a provider immediately who will help them transition to their own insulin regimen safely.

Test Run Policies Only

- Subjects in the Test Run period will be under supervision of study staff during the day. Subjects will be allowed to leave the clinic but will be restricted to the area immediately surrounding the clinic (e.g. within walking distance) and must be in contact with study staff regarding their location.
- While in the clinic, there will be no restrictions on physical activity and subjects will be encouraged to remain as physically active as they are in their normal life.
- Subjects will be required to check a BG at 1 and 2 hours after each meal announcement on all three days of the Test Run, including meal challenges and any other meal announcements delivered.
- Subjects will complete the meal challenges on days 2 and 3 of the Test Run period, following the same protocol as the RCT portion of the study.
- Subjects will be discharged from the clinic at the end of each day to home with a designated contact. During the first two nights at home, subjects will be instructed to check an overnight BG.

V. d. iv. Remote Monitoring

Local Alarms

- All alarm settings will be the same for the Test Run, the RCT portion of the study and during meal challenges.
- Alarms will sound and a visual alert will appear on the screen of the G5 mobile app when the CGM glucose is ≤ 70 mg/dl and the BP will alarm when the CGM glucose is ≤ 50 mg/dl.
 - Participants will be trained to test their BG with the study glucometer in response to such an alarm and take any necessary measures to treat hypoglycemia.

- Participants will be trained on troubleshooting for various scenarios that could lead to low threshold alarms. For instance, a threshold alarm could be due to true hypoglycemia, inaccurate CGM readings, or a compression artifact at the site of the sensor.
 - The first step for all glucose-related alarms will be to perform a fingerstick BG measurement.

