 - If the BG measurement is not consistent with the fact that a threshold alarm has occurred, then the participant will assess the accuracy of the CGM, and the possibility of a compression artifact (they will be trained in the causes and recognition of these events). If a compression artifact is suspected, they will take steps to relieve the pressure on the transmitter. If no compression is suspected, the participant will calibrate the CGM.
 - If the BG measurement is consistent with a low threshold alarm, the participant will treat hypoglycemia with carbohydrate ingestion according to their usual practice. Study staff will recommend the standard of care, 15 grams of rapid acting carbohydrates and re-testing BG in 15 minutes. Study staff will recommend the participant continue to monitor their BG until it returns to normoglycemia, and to contact study staff with any questions or concerns.
- Alarms will sound and a visual alert will appear on the Dexcom CGM app if CGM glucose is > 250 mg/dl.
 - Participants will be trained to test their BG with the study glucometer (provided) and the ketone level with the study ketone meter (provided) in response to such an alarm and take necessary measures to treat the hyperglycemia.
 - Participants will be trained on troubleshooting for various scenarios that could lead to persistent or severe hyperglycemia. For instance, hyperglycemia could be due to true hyperglycemia (caused by a missed insulin dose or a failed infusion set for example) or inaccurate CGM readings.
 - The first step in responding to severe or persistent hyperglycemia according to the CGM will be to perform a fingerstick BG and ketone measurement.
 - If the BG measurement is not consistent with the CGM readings, the participant will calibrate the CGM.
 - If the BG measurement is consistent with the CGM readings:
 - Participants will be asked to investigate their insulin infusion set and consider replacing it, check for any occlusions along the insulin fluid path, and check to make sure that the insulin cartridge is not empty.
 - Study staff will recommend the participant continue to monitor their BG until it returns to normoglycemia, and to contact study staff with any questions or concerns.
 - If ketones ≥ 0.6 mmol/L are present:
 - Participants will be advised to change their pump infusion set and will be reminded that the BP should dose insulin accordingly.

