 - Study staff will recommend the participant continue to monitor their ketone levels and BG every 60 minutes until ketones return to < 0.6 mmol/L and BG is < 180 mg/dl, and to contact study staff with any questions.
 - If participants experience persistent hyperglycemia lasting more than 2 hours, they will be instructed to contact study staff for consideration of infusion set replacement and/or correction insulin according to the above protocol.

Remote Monitoring

- All remote monitoring will be the same for the Test Run, the RCT portion of the study and during meal challenges.
- There will be at least one provider (MD or NP) on call at all times. Additional study staff members may assist with on-call duties. Subjects may contact study staff as necessary for help troubleshooting

- any issues that may arise
- An alert will be generated if remote monitoring indicates that a participant is offline.
 - If there are no indications of device malfunction as the cause for lost connectivity, the glucose level is in safe range, and a participant chooses to remain in an area with poor network coverage, we will instruct the participant to check the BP display or CGM at least every 20 minutes for alert icons and to be aware that we are unable to monitor for severe lows or highs at this time.
 - We will call the participant every 2 hours to check on safety and device function until remote monitoring is restored.
- The remote monitoring system will generate an alarm if the CGM glucose is < 50 mg/dl for 15 minutes.
 - When an alert comes to the monitoring station, a study staff member will contact the participant on any of the provided phone numbers. If staff remains unable to contact the participant, they will call the designated contact on any of the provided phone numbers.
 - Study staff will verify the participants are aware of the hypoglycemia and taking action to treat it. Participants will be reminded of the protocol for hypoglycemia, and the study provider will ensure they understand and will follow study procedures. Participants will be encouraged to follow up with any questions or concerns. All contact with the participants in response to hypoglycemia alarms will be documented.

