 - In the case of a low threshold alarm with no response from the participant and no success in locating them or their designated contact, the site principal investigator will be immediately informed. If remote monitoring shows ongoing hypoglycemia, a decision may be made to dispatch emergency medical services to the locations the participant is known to frequent.
 - Remote monitoring for hypoglycemia will be the same in all study arms.
- The remote monitoring system will generate an alarm if the CGM glucose is > 300 mg/dl for 90 minutes.
 - Participants will be reminded of the protocol for prolonged hyperglycemia, and the study provider will ensure they understand and will follow study procedures. Participants will be encouraged to follow up with any questions or concerns. All contact with the participants in response to hyperglycemia alarms will be documented.
 - Remote monitoring for hyperglycemia will be the same in all study arms.
- If there is a technical problem with the bionic pancreas that cannot be resolved over the phone, a member of study staff may be dispatched to the location of the subject to provide in-person assistance. The subject may be asked to come to the Diabetes Research Center or study staff may meet them in another public place. If this is not possible or would be too disruptive (i.e. in the middle of the night) the subject will be asked to take over their own glycemic control using their insulin pump until such time as a meeting can be arranged for in-person inspection of the device. This should occur in most cases within 12 hours. Staff will not go into subjects' houses or other non-public places; nor will they go to any place to meet the subject that is not public or where they do not feel safe.

V. d. v. Visit Procedures

Test Run Visit Procedures

Day 1:

- The body weight of the subject will be documented.
- A urine pregnancy test will be performed in female volunteers at the start of the Test Run. If the test is positive the volunteer will be informed of the result and the visit will be ended. The date of the last menstrual period will also be documented.
- Study staff will review any changes in the participant's medical history or medications to ensure continued eligibility, and any adverse events that may have occurred since their screening visit.

- The subjects will place a Dexcom G5 sensor and study staff will confirm they are doing it properly.

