- Subjects may contact a study provider (MD or NP) for advice at any time, and may contact the troubleshooting support team, as they wish. Subjects will be assisted in checking the bionic pancreas for any malfunction and correcting any problems that are found.
- If no correctable fault is found, but there is doubt regarding the correct function of the bionic pancreas system, an entirely new backup bionic pancreas system may be brought to the subject's location by study staff.
- If a subject experiences diabetic ketoacidosis requiring hospitalization during the study, his or her participation in the study will be discontinued.

V. d viii. Response to Other Medical Needs

If the subject experiences any non-emergent medical concerns outside the scope of diabetes care, he or she will see their personal physician. If the subject experiences urgent or emergent medical concerns outside the scope of diabetes care and their primary care physicians, they should visit a walk-in clinic or emergency room, or if necessary call 911.

V. d. ix. Monitoring of Bionic Pancreas Performance

Collaborators from Beta Bionics will be readily available by phone for consultation at all times during the course of each experiment. Their team of engineers will train study staff on the appropriate use of the iLet and provide support as needed.

V. d. x. Supervision by Study Staff

A study provider (MD or NP) will be on call at all times during the course of all study arms. All trained staff will have the capability of remotely viewing glucose information to facilitate troubleshooting with subjects and decide whether additional assistance is needed. Subjects in the Test Run period will be under close supervision by study staff during the day on each of the three days.

VI. Biostatistical Analysis

VI. a. Data Collected

VI. a. 1. Prior to start of experiment:

- Age
- Sex
- Race and ethnicity
- Date of last menstrual period in female subjects
- Date of diabetes diagnosis
- Medical, surgical, and social history, allergies, and review of systems relevant to inclusion and exclusion criteria
- Medications (prescription and non-prescription) and date of last change in medication regimen
- Duration of insulin pump use
- Type of insulin used in pump
- Insulin regimen (basal rate, sensitivity factor, and carbohydrate ratio)
- Average total daily dose of insulin in the last 30 days as available
- History of exposure to non-human insulin or insulin analogs (type, timing, duration)

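### No ketone reading, however high, by itself requires a participant to call study staff; the hyperglycemia contact rules depend on glucose alone

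*Combined protocol and SAP*

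**What the plan says.** The ketone instructions are in V.d.iv, under Local Alarms. The Dexcom app alarms above 250 mg/dl, and the participant then measures fingerstick glucose and ketones. For ketones of 0.6 mmol/L or more, two steps follow:

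- "Participants will be advised to change their pump infusion set and will be reminded that the BP should dose insulin accordingly".
- Staff recommend checking ketones and glucose every 60 minutes "until ketones return to < 0.6 mmol/L and BG is < 180 mg/dl, and to contact study staff with any questions".

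The next rule concerns duration: "If participants experience persistent hyperglycemia lasting more than 2 hours, they will be instructed to contact study staff". The contact is so that a new infusion set, correction insulin or both can be considered. That sentence gives neither a ketone level nor a glucose cut-off. Under Remote Monitoring in the same section, "The remote monitoring system will generate an alarm if the CGM glucose is > 300 mg/dl for 90 minutes".

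V.d.vii (Response to Hyperglycemia) names no ketone level and makes contact optional: "Subjects may contact a study provider (MD or NP) for advice at any time, and may contact the troubleshooting support team, as they wish". V.d.x states that "A study provider (MD or NP) will be on call at all times during the course of all study arms". The only other ketone figure in the plan, above 1.5 mmol/L, is one component of the DKA definition in IX.b and IX.c. There it classifies events and is not an instruction to call anyone.

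**The concern.** Under this plan a ketone reading of 0.6 mmol/L and one far above 1.5 mmol/L lead to the same instructions. Whether staff must hear about it depends on how long glucose stays high, or on CGM passing 300 mg/dl. Yet the stopping rule for hourly re-testing requires both ketones and glucose to come down, so the plan itself treats ketones as a separate matter from glucose.

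The stake is participant safety first and trial continuity second. Under IX.b, one DKA hospitalization ends a subject's participation. More than one withdrawal for DKA hospitalization, or for seizure or unconsciousness with hypoglycemia, stops the study until the DSMB votes to restart it. The plan already uses mandatory immediate contact elsewhere: V.d.iii requires it after inadvertent acetaminophen use. A ketone reading above the plan's own DKA component has no such rule.

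**Working it through.** The plan gives no figure to reproduce, so the check is mainly a comparison of the contact rules, followed by simple timing.

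**Step 1. What triggers each safeguard**

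| Safeguard | Trigger | Triggered by ketones? |
|---|---|---|
| Local alarm, then glucose and ketone test (V.d.iv) | CGM > 250 mg/dl | No |
| Set change and hourly re-tests (V.d.iv) | Ketones ≥ 0.6 mmol/L | Yes, but contact only for questions |
| Instructed call (V.d.iv) | Hyperglycemia > 2 hours | No |
| Remote alarm (V.d.iv) | CGM > 300 mg/dl for 90 min | No |
| Advice from a provider (V.d.vii) | Participant's choice | No |
| Designated contact (IV.b) | Symptoms; training on when to call | No ketone value given |

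Number of ketone values that by themselves require a call: 0. The bullet nesting in V.d.iv is not fully recoverable from the extracted text, but under either nesting the instructed call depends on duration of hyperglycemia.

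**Step 2. Glucose held at 251-300 mg/dl, ketones above 1.5 mmol/L**

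The remote alarm does not fire in this range, so only the 2-hour rule applies.

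Wait from the > 250 mg/dl alarm = 120 min − minutes already counted before the alarm.

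- Clock starts at the alarm: 120 − 0 = 120 min.
- Clock starts at 180 mg/dl, rise of 2 mg/dl/min (both assumed): (250 − 180)/2 = 35 min; 120 − 35 = 85 min.
- Clock starts at 180 mg/dl, rise of 1 mg/dl/min (both assumed): (250 − 180)/1 = 70 min; 120 − 70 = 50 min.

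These waits run from the alarm. They equal the wait from the high ketone reading only if ketones already exceed 1.5 mmol/L at the first test. If the first such reading comes at the 60-minute re-test, what remains is 120 − 60 = 60 min or 85 − 60 = 25 min. In the 50-minute case the call is due before that re-test.

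**Step 3. Glucose falls within 2 hours, ketones stay high**

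The 2-hour condition is not met. The remote alarm is silent unless CGM had already been above 300 mg/dl for 90 minutes. Hourly re-testing continues because ketones are still ≥ 0.6 mmol/L, with no time limit and no required call. This result needs no assumption about rise rates.

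**The case against.** The strongest reply is that the plan acts well below 1.5 mmol/L. At 0.6 mmol/L it already advises a set change and hourly testing until both measures recover, so what is missing is notification, not detection or first response. Participants have used a pump for at least 6 months. DKA in the last 6 months is an exclusion. For designated contacts, "They will also be trained to recognize the symptoms of hyperglycemia, and when to contact study staff and local EMS". The wording that staff will recommend monitoring might also suggest that staff are already involved. All of this lowers the severity, but none of it makes a ketone value a reason to call, and no step in the ketone branch requires staff contact.

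It is also fair to say that 1.5 mmol/L comes from a composite DKA definition that includes symptoms, acidosis and treatment in a facility. The documents do not establish it as a home action level, so it is usable only as a notification trigger.

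Three stronger readings are tempting and should not be drawn:

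- *That Test Run nights have almost no protection.* V.d.iii says "During the first two nights at home, subjects will be instructed to check an overnight BG", but that check is an addition. V.d.iv and V.d.vii apply the same alarms, remote monitoring and hyperglycemia response to the Test Run, and subjects go home with a designated contact.
- *That the gap is particular to BC222.* It is identical for all three insulins, and the BC222-specific risk raised in section VII is hypoglycemia.
- *That the fix cuts a 50-120 minute wait to zero.* Those minutes run from the glucose alarm, while an immediate call runs from the ketone reading. The lower figures also rest on assumptions the documents do not supply.

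**Conclusion.** The point holds as a modest safety gap. Following V.d.iv as written, no ketone level alone obliges a participant to tell staff. With glucose at 251-300 mg/dl, the time without a required call is at most about 2 hours from the > 250 mg/dl alarm, taking the clock to start no later than that alarm. If glucose settles within 2 hours and ketones do not, there is no required call at all. That second case is the firmer part of the finding. Ketones are not a planned endpoint, so no trial conclusion is affected. This is a change the sponsor should make because it is cheap and specific; it is not a fault in the analysis.

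**What to change.** Add one sentence to the ketone step in V.d.iv and to participant training: *For any ketone reading > 1.5 mmol/L, call the on-call study provider immediately.* Apply it in the Test Run and all RCT arms, including nights and meal challenges. The value is the ketone component of the plan's own DKA definition and serves only to trigger notification; treatment stays with the provider.

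The meter and the on-call provider are already in place. The cost is a few extra calls, some at night. The documents give no rate of such readings. For scale only, maximum exposure is 30 × 3 × 7 + 4 × 3 = 642 person-days; an assumed 0.2 to 1 reading per 100 person-days would give 642 × 0.002 = 1.3 to 642 × 0.01 = 6.4 calls.

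Optional and separate: have V.d.vii refer to V.d.iv, and name ketone readings in the data list in VI.a.2. Any summary by insulin should be descriptive and shown beside the number of tests, since counts depend on how often participants test.
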